11. APPENDICES

11.1. Appendix 1: Protocol Deviation Management and Definitions for Per Protocol Population

Major protocol violations could impact the ability to assess efficacy and the primary endpoint for the study. A participant meeting any of the following criteria will be excluded from the Per Protocol population:

Number	Exclusion Description
01	Participant does not have a scheduled parasitology assessment within window for any of the Day 1-14 ¹ , Day 21, Day 28, Day 60, Day 90, Day 120, Day 150 or Day 180 visits prior to first relapse or end of study (early withdrawal or end of follow-up) ² .
02	When in the clinic on Days 1 to 14, participant vomited a dose of study medication and either vomited the redose, or a redose was not given. Or participant did not take required number of DHA-PQP tablets on Days 1-3.
03	Violation of any of the following entry criteria: Participant had a severe malaria infection (exclusion #1) Participant had severe vomiting or diarrhoea (exclusion #2) Participants liver function test was > 2 x ULN (exclusion #4)
04	The participant has taken/received: Anti-malarials (e.g., artemisinin-based combination therapies (ACTs), mefloquine, primaquine, quinacrine) or drugs with anti-malarial activity within the past 30 days. Treatment with any investigational drug within 30 days of study entry, or within 5 half-lives, whichever is longer. A concomitant medication with an anti-malarial activity prior to first relapse or end of study (early withdrawal or end of follow-up). A list of all concomitant medications will be reviewed by a GSK clinician prior to unblinding the study, and classified accordingly
05	Participant did not take blinded study medication with food on Days 1-3.
06	Participant who met study treatment withdrawal criteria, as defined in protocol Section 5.4, but was not withdrawn from study treatment.
07	Participant received incorrect treatment.
08	Participants taking dose outside of the clinic that was not observed by a site staff member.

¹ For the twice daily blood smears on days 1-3, when determining exclusion from the PP population, participants were excluded if they didn't have at least one assessment on each day, without having first demonstrated clearance. The time of the assessments will not be used since visit windows around the 6-12 hour duration have not been defined.
 
² On study days 1-3, participants were scheduled to have twice daily blood smears until they had two consecutive negative smears, 6-12 hours apart. Due to errors in the parasite counts, 3 participants (participant numbers P_n PP and PP) were incorrectly concluded to have negative smears which were in-fact positive, and hence missed a subsequent parasitology assessment during days 1-3. These participants will not be excluded from the PP population as a result of this missed assessment.
	

During the study, the data is reviewed on an ongoing basis, with protocol deviations (PDs) identified by programmatic checks and manual review. These deviations are

assessed by data management and clinical (with input from others as required), and are entered into the deviations log, with the 'Important' flag set accordingly.

The per protocol population exclusion flag is a derived variable in the analysis and reporting dataset (ADaM.ADDV). This variable is not captured in the SI or SDTM datasets. As for the 'important PD' flag, data is reviewed throughout the study to identify participants who should be excluded from the PP population. At DBR, additional programmatic checks are performed by the clinical programming team to further check for PDs. A spreadsheet of any PDs identified is provided to data management and clinical, who will add them to the deviations log with appropriate flags if not already included.

A listing will be produced for the safety population showing the individual participant numbers for each important protocol deviation. A table will be produced showing the number and percentage of participants with major protocol deviations, overall and by type of deviation.

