### **Premature Withdrawal of Study Treatment**

If a subject prematurely discontinues from study treatment for any reason or reaches the primary endpoint of relapse, they should continue to attend study visits to Day 180. The reason for withdrawal from treatment should be recorded in the electronic case record form (eCRF). Given the long half life of tafenoquine, the maximal pharmacodynamic effects such as potential hemolysis or methemoglobinemia may occur several days after completion of dosing. These data will be recorded, as they comprise an essential evaluation that needs to be done before discharging any subject from the study. Therefore, the investigator should continue following subjects for all protocol assessments, up to and including Day 180 whenever possible. The subject should be given appropriate rescue therapy according to local treatment guidelines if they develop a malarial recurrence (see Section 6.9.1.2).

Subjects should discontinue taking study treatment if they meet **any** of the criteria below:

- Intolerable AEs:
  - Any grade 4 AE or toxicity in the absence of compelling evidence that the AE is not related to investigational product(s)
- Clinically significant laboratory results considered by the investigator to warrant withdrawal from the study treatment
- Liver chemistry stopping criteria (refer to Section 5.4.1 and Section 12.2 Appendix 2)
- Hemoglobin stopping criteria: Given the hemolytic potential of TQ and PQ in subjects with G6PD deficiency, study specific hematologic stopping criteria will be employed (refer to Section 5.4.2)
- QTc stopping criteria (refer to Section 5.4.3)

When QT or hemolytic stopping criteria are met, this must be promptly reported by the investigator to GSK as a Serious Adverse Event (see Section 7.5)

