4. ANALYSIS POPULATIONS

Population	Definition / Criteria	Analyses Evaluated
Screened	All participants who were screened for eligibility.	Study Population
Enrolled	All randomised participants.	Study Population
Safety	All randomised participants who received at least one dose of blinded study treatment. If participants receive a treatment different to their randomized treatment, they will be	Study Population Safety

Population	Definition / Criteria	Analyses Evaluated
	analysed according to the treatment actually received.	
Safety Open Label, PQ phase, Non-Relapsers (Safety OL)	All participants in the safety population who did not relapse during the double-blind phase and went onto the open-label primaquine phase at the end of the study.	Study Population Safety
Microbiologic-Intent-To-Treat (mITT)	All randomized participants who received at least one dose of blinded study treatment and have microscopically-confirmed P. vivax parasitaemia at baseline. Participants will be analysed according to their randomized treatment.	Efficacy
Per-Protocol (PP)	All participants in the mITT population for whom there were no major protocol deviations that impact the primary endpoint. Protocol deviations that would exclude participants from the PP population are defined in Section 4.1 (Protocol Deviations) and Appendix 1 (Protocol Deviation Management and Definition for Per-Protocol Population).	Sensitivity/ supporting analyses of efficacy data
PK population	All participants for whom at least one systemic tafenoquine concentration, and associated sample date/time is available.	PK

NOTES:

Please refer to [Appendix 11](#): List of Data Displays which details the population to be used for each display being generated.

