11.6.2. Study Population

Demographics
Body Mass Index (BMI)
Calculated as Weight (kg) / [Height (m) ²]

Baseline Fever
A participant is considered to have had a fever at baseline if they have a temperature recorded in their vital signs data >37.4°C at any point prior to the first dose of study medication (including DHA-PQP).

Prior and Concomitant Medications

Medications will be coded using the latest version of GSK Drug. Prior medications = medications taken within the 30 days prior to the date of the first dose of DHA-PQP. Any medications with stop dates earlier than 30 days before the date of the first dose of DHA-PQP will not be reported in tables and listings. Concomitant medications = medications with start date on or after the start date of the first dose of DHA-PQP, or ongoing on the start date of the first dose of DHA-PQP. Medications taken prior to the study and continuing during the study will be summarised as both prior medications and concomitant medications. See Section 11.7.2.1 for the handling of missing and partial dates.

Treatment Compliance

All study medication should be administered in the presence of the Investigator or study nurse, and ingestion confirmed. On any day of in clinic dosing, a participant will be classified as compliant with daily administered dose if they do not vomit the initial dose or if they are successfully re-dosed. A participant is considered to be compliant with blinded medication if they successfully administer 12 doses of blinded PQ study medication and a single dose of blinded TQ medication (note, the blinded medication does not need to have been observed for a subject to be considered compliant). Participants who were randomized but did not report a treatment start date will be categorised as having zero doses.

Treatment Compliance

PQ / PQ placebo blinded treatment compliance will be calculated based on the formula:

$$\text{PQ / PQ placebo Blinded Treatment Compliance} = \text{Number of Actual doses} / 14$$

Compliance could be greater than 100% if there are events of overdose.

The number of participants taking <12 or \geq 12 doses of PQ/PQ placebo will also be summarised.

TQ / TQ placebo compliance will be summarised as if they successfully administered the dose (yes/no).

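### The per-protocol set has no minimum number of blinded doses: an under-dosed primaquine participant stays in, while one vomited dose that is not successfully replaced excludes

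*SAP*

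**What the plan says.** Protocol 9.3.1 leaves the definition of major violations to the analysis plan. SAP Section 4 restricts the PP set to mITT participants with "no major protocol deviations that impact the primary endpoint" and points to Appendix 1, which lists eight exclusions. Those that touch on dosing are:

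- **02, vomiting:** on Days 1 to 14, the "participant vomited a dose of study medication and either vomited the redose, or a redose was not given".
- **02, dose count:** "participant did not take required number of DHA-PQP tablets on Days 1-3".
- **05, dosing with food:** "Participant did not take blinded study medication with food on Days 1-3".
- **Exclusion number 06, failure to stop when the stopping rules applied:** "Participant who met study treatment withdrawal criteria, as defined in protocol Section 5.4, but was not withdrawn from study treatment".
- **07:** wrong treatment received.
- **08:** a dose taken away from the clinic and not seen by staff.

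Exclusion 01 concerns missed parasitology assessments, 03 concerns entry criteria, and 04 concerns other drugs.

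SAP 11.6.2 defines compliance separately. A participant is compliant with blinded treatment "if they successfully administer 12 doses of blinded PQ study medication and a single dose of blinded TQ medication". The footnote to mock shell POP_T3 makes clear that this means 12 or more, and the shell tabulates fewer than 12 against 12 or more. The definition feeds summaries and listings only; PP membership does not use it.

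SAP 7.1.5.1 repeats the primary analysis in the PP set, with hazard ratios for all three treatment comparisons. Of participants who stop treatment early, Protocol 5.4 says "they should continue to attend study visits to Day 180".

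**The concern.** The PP rules respond to how a single dose was lost, not to how much treatment was received. One capsule vomited and not replaced excludes; eleven capsules never taken do not. Exclusion 08 shows the same inversion: a dose swallowed unobserved outside the clinic excludes, while a dose never swallowed does not.

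This matters mainly for PQ, because TQ is a single dose and PQ is a 14-day course. Stopping early loses active drug only in the PQ arm. If such participants stay in the PP set, its PQ estimate is pulled towards control. That weakens PQ versus DHA-PQP alone, the objective added in Amendment 1 at the Indonesian regulator's request, and tilts TQ versus PQ towards TQ.

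The PP analysis is also the natural place to look for sensitivity to under-treatment. SAP 7.1.4 aims at the effect had everyone remained on randomised treatment, but handles those who discontinue like those who continue.

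**Working it through.** **Rule check.** Four hypothetical participants, each starting blinded treatment on Day 1, attending every visit and otherwise deviation-free:

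1. *Dosed with food on Days 1 to 3, then stops: 3/14 doses.* Exclusion 01 is not met, because visits continue and the remaining scheduled smears (Days 7, 14, 21 and so on, Protocol 7.4) are taken. Exclusion 02 is not met: nothing was vomited and the DHA-PQP was complete. Exclusion 05 is not met: Days 1 to 3 were dosed with food. Exclusion 06 is not met: it removes those who should have stopped but did not. Exclusions 03, 04, 07 and 08 do not apply. **Stays in PP; non-compliant under 11.6.2.**
2. *Dosed with food only on the smear days 1, 2, 3, 7 and 14: 5/14 = 36%.* By the same reasoning, **stays in PP; non-compliant.**
3. *13/14 doses, one vomited and not successfully replaced.* Exclusion 02 is met. **Removed from PP; compliant under 11.6.2.**
4. *14/14 doses, one taken outside the clinic unobserved.* Exclusion 08 is met. **Removed from PP; compliant under 11.6.2**, which does not require observation.

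The compliance threshold is 12/14 = 86%. In these four cases the PP rules and the SAP's own compliance definition give opposite answers.

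**Design figures (Protocol 9.2.1).** Relapse-free rates are 50% (DHA-PQP alone), 85% (PQ) and 85% (TQ), with 50 per arm and 10% withdrawal. Expected relapses: 25 + 7.5 + 7.5 = 40, and 40/150 = 26.7%, as stated. For the primary comparison, HR = ln(0.85)/ln(0.50) = 0.2345. With 45 evaluable per arm, events are 45 × 0.50 + 45 × 0.15 = 29.25. Power is 91.8% (Freedman), 95.6% (two proportions) or 97.5% (Schoenfeld), so the stated figure of more than 90% is reproduced. The gap in Appendix 1 changes none of these.

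**Size of the dilution.** Let f be the share of the PP PQ arm that is under-dosed and r the share of the 35-point benefit they keep:

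PQ relapse-free rate = 0.85 − 0.35 × f × (1 − r)

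Under proportional hazards, HR of TQ versus PQ = ln(0.85)/ln(PQ rate), and HR of PQ versus control = ln(PQ rate)/ln(0.50). The documents give neither f nor r. Assumed range: 1 to 5 of 50, with r = 0 or 0.5.

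- f = 1/50, r = 0: 0.85 − 0.35 × 0.02 = 84.3%; TQ:PQ HR 0.95; PQ:control HR 0.246.
- f = 5/50, r = 0: 0.85 − 0.35 × 0.10 = 81.5%; TQ:PQ HR 0.79; PQ:control HR 0.295.
- f = 1/50, r = 0.5: 84.65%; TQ:PQ HR 0.975; PQ:control HR 0.240.
- f = 5/50, r = 0.5: 83.25%; TQ:PQ HR 0.89; PQ:control HR 0.264.

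Without under-dosing the values are 85%, 1.00 and 0.2345. In expected relapses the change with r = 0 is 0.35 per under-dosed participant: 0.35 for one, 1.75 for five. For scale, the 95% half-width around 15% in 50 participants is 1.96 × √(0.15 × 0.85/50) = 9.9 points.

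**The case against.** The strongest defence is that following the stopping rules is adherence to the protocol. Protocol 5.4 requires treatment to stop in defined safety situations and asks for continued follow-up. Exclusion 06 removes those who did not obey. A PP set that keeps correct early stoppers is coherent, and defining it by dose received is partly a choice. That stands as a reason the sponsor could state, but the SAP does not state it. It also does not explain why a participant who simply misses capsules stays in when one unreplaced vomited capsule excludes.

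Other points limit the impact. Dosing is directly observed at the site, so large shortfalls should be rare. The PP analysis is supportive, its only listed p-value in SAP 7.1.5.1 is for TQ versus DHA-PQP alone, and Protocol 2.1.4 treats PQ as an informal benchmark. Under-dosing will be visible in Tables 1.2 and 1.32 and in Listing 37. All of this stands, and none of it supplies the criterion.

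Three stronger readings are not supported:

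- *Any vomited blinded dose excludes.* It does not: a successful redose keeps the participant in the PP set and compliant.
- *The primary comparison is diluted.* It is not: after the single TQ or placebo dose, every capsule in those two arms is placebo. What remains there is that the TQ dose is not explicitly required. Exclusion 05 can be read as catching a participant with no blinded dose on Days 1 to 3, and exclusion 02 catches a vomited, unreplaced one.
- *The PP set as a whole fails to represent treatment as planned.* The exposure is confined to the PQ arm.

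**Conclusion.** The point holds in limited form. As written, Appendix 1 can remove a participant with 13 or 14 of 14 doses and keep one with 3 of 14, because it has no minimum-dose criterion for blinded treatment and does not use the compliance variable the SAP already derives. The consequence is possible dilution of the PQ arm in two supportive PP comparisons, in a direction that favours TQ over PQ. Sample size, power and the mITT primary analysis are unaffected.

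If 1 to 5 of 50 PQ participants are under-dosed with no retained benefit, the PP PQ relapse-free rate falls by 0.7 to 3.5 points and the TQ:PQ hazard ratio moves from 1.00 to between 0.95 and 0.79. With half the benefit retained, the hazard ratio lies between 0.975 and 0.89. These shifts are well inside sampling error. The count of under-dosed participants is an assumption, and no retained benefit is the worst case. Under direct observation the real effect is probably near the small end.

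**What to change.** Before unblinding, add one row to Appendix 1, applied identically in all arms. It would exclude participants who do not meet the 11.6.2 compliance definition, meaning fewer than 12 successful PQ/placebo doses or no successful TQ/placebo dose, except where dosing was cut short by a relapse. The exception is essential. Smears are scheduled on Days 7 and 14, and recurrence by Day 14 is itself an efficacy outcome, so a plain count of doses before first relapse would delete early failures because they failed. If the sponsor prefers to keep participants who stopped under the protocol's own rules, Appendix 1 should say so and give the reason.

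The cost is one row, using a variable already derived. The downside is that a few TQ or control participants may leave the PP set for missing placebo capsules, with no gain in treatment fidelity in those arms. That is the price of a rule that can be applied blind and equally across arms.

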11.2. Appendix 2: Schedule of Activities

11.2.1. Protocol Defined Schedule of Events

Procedures	Visit Day (Treatment Period Days 1-14)																
	1	1		2 ^b	3	4	5	6	7	8	9	10	11	12	13	14	
	Pre DHA-PQP	DHA-PQP	Blinded med ^a														
Written Informed Consent	x																
Subject Demography	x																
Medical History	x																
Disease History	x																
Signs & Symptoms	x	x															
Therapy History	x																
Inclusion/Exclusion Criteria	x																
Efficacy Assessments																	
Blood smears	x			x ^c	x ^c				x								x
Plasmodium PCR genotyping/sequencing	x																
Safety Assessments																	
Concomitant Medication	x		x	x	x	x	x	x	x	x	x	x	x	x	x	x	x
Physical Examination	x			x	x			x									
Vital Signs ^d	x			x	x ^o			x									x
12-lead ECG ^e	x				x			x									
Adverse Events ^f			x	x	x	x	x	x	x	x	x	x	x	x	x	x	x
Serious Adverse Events ^g	x		x	x	x	x	x	x	x	x	x	x	x	x	x	x	x
G6PD (phenotyping) ^h	x																
G6PD/CYP2D6 (genotyping) ⁱ	x																
Laboratory Assessments																	
Hematology/Clin.Chem/urinalysis ^j	x				x		x		x								x
Methemoglobin ^l	x			x	x	x	x	x	x	x	x	x	x	x	x	x	x
PK sampling	x		x ^k					x									x
Investigational Product																	
Dispense Open Label DHA-PQP		x		x	x												
Dispense Blinded Study Treatment (access IWRS on day 1 only)			x	x	x	x	x	x	x	x	x	x	x	x	x	x	x

CONFIDENTIAL

200894

Procedures	Visit Day (Follow Up Period)									
	21	28	60	90	120	150	180	195 ^p (only for subjects who have not relapsed prior to Day 180)	Relapse	Withdrawal from study
Window	-/+3d	-3d, +15d	-16 d, +15d	-14d, +15d	-14d, +15d	-14d, +19d	-/+10d	Day 180 + 15d to 21d		
Efficacy Assessments										
Parasitological Assessment (blood smears)	x	x	x	x	x	x	x		x	x
Plasmodium PCR genotyping/sequencing									x	
Safety Assessments										
Concomitant Medication	x	x	x	x	x	x	x	x	x	x
Physical Examination	x	x	x	x	x	x	x		x	x
Vital Signs ^d	x	x	x	x	x	x	x		x	x
12-lead ECG ^e		x							x	x
Adverse Events	x	x	x	x	x	x	x	x	x	x
Serious Adverse Events	x	x	x	x	x	x	x	x	x	x
Dispense rescue treatment (ACT+PQ)									x	
Laboratory Assessments										
Hematology/Clinical Chemistry	x	x	x	x	x				x ^m	x ^m
Methemoglobin ^l	x	x	x						x	x
PK Sampling		x	x						x ⁿ	
Open Label Primaquine										
Dispense open label PQ –only for subjects who have not relapsed prior to D180							x			

Time and Event Table Notes:

- a) Blinded study treatment may be started on Day 1 or Day 2. If started on Day 2, blinded primaquine/placebo is given from Day 2-15.
- b) If a subject starts blinded study treatment on Day 2, the following assessments should be completed on Day 15: Concomitant medication, AEs/SAEs, methemoglobin, dispense blinded study treatment.
- c) Blood smears to be taken twice daily until two consecutive negative smears 6-12 hours apart.
- d) Vital signs include height and weight (screening only), blood pressure, temperature, heart rate and respiratory rate.
- e) ECGs will be done in triplicate on Day 1 (prior to DHA-PQP). Subsequent ECGs will be done as single ECGs unless prolonged QTcF is seen. ECG timings post baseline will be as follows: 1) Before the last of the three daily doses of DHA-PQP 2) 4 hours (window -1 to +2 hours) after last dose of DHA-PQP, 3) Day 7, 4) Day 28 and 5) relapse/withdrawal if within 28 days post-dose.
- f) Adverse events are recorded from the time of the first dose of study treatment.
- g) Serious adverse events are recorded from the time of consent in order to fulfil international regulatory requirements.
- h) G6PD phenotyping to be performed by suitable qualitative test (refer to SRM) and quantitative spectrophotometric analysis.
- i) Blood sample to be collected for CYP2D6 genotyping and stored for possible G6PD genotyping. Sample for G6PD genotyping may be analyzed in the event of an SAE due to hemoglobin decline where a repeat G6PD phenotype assay would not define G6PD status (e.g. transfusion given or high reticulocyte count).
- j) Dipstick urinalysis to be only done at screening.
- k) PK samples must be taken 6-12 hours and 24-48 hours post blinded dose of tafenoquine.
- l) Methemoglobin will be measured daily up to Day 14, alternate days up to Day 28 and on Day 60.
- m) Hematology/clinical chemistry to be done at relapse/withdrawal (up to Day 120 only).
- n) PK will be done as close to the time of relapse as possible (up to Day 60 only).
- o) Vital signs on Day 3 will be done immediately after ECGs (ie before the last of the three daily doses of DHA-PQP and 4 (-1 to +2) hours after the last dose of DHA-PQP).
- p) The D195 assessment is only required for subjects who do not relapse prior to D180 and receive open label primaquine (0.5mg/kg daily for 14 days) at the end of the study. Subjects who have relapsed prior to Day 180 will complete the study at D180.

11.3. Appendix 3: Assessment Windows

11.3.1. Definitions of Assessment Windows for Analyses

Analysis Set / Domain	Parameter (if applicable)	Target	Analysis Window		Analysis Timepoint
			Beginning Timepoint	Ending Timepoint	
miTT, PP, Safety	All	Day 1	Day 1	Day 1	Day 1
miTT, PP, Safety	All	Day 2	Day 2	Day 2	Day 2
miTT, PP, Safety	All	Day 3	Day 3	Day 3	Day 3
Safety	ECG	4 hours after last DHA-PQP dose	3 hours after last DHA-PQP dose	6 hours after last DHA-PQP dose	4 hours after last DHA-PQP dose
miTT, PP, Safety	All	Day 4	Day 4	Day 4	Day 4
miTT, PP, Safety	All	Day 5	Day 5	Day 5	Day 5
miTT, PP, Safety	All	Day 6	Day 6	Day 6	Day 6
miTT, PP, Safety	All	Day 7	Day 7	Day 7	Day 7
miTT, PP, Safety	All	Day 8	Day 8	Day 8	Day 8
miTT, PP, Safety	All	Day 9	Day 9	Day 9	Day 9
miTT, PP, Safety	All	Day 10	Day 10	Day 10	Day 10
miTT, PP, Safety	MetHB	Day 11	Day 11	Day 11	Day 11
miTT, PP, Safety	MetHB	Day 12	Day 12	Day 12	Day 12
miTT, PP, Safety	MetHB	Day 13	Day 13	Day 13	Day 13
miTT, PP, Safety	MetHB	Day 14	Day 14	Day 17	Day 14
miTT, PP, Safety	All except MetHB	Day 14	Day 11	Day 17	Day 14
miTT, PP, Safety	All	Day 21	Day 18	Day 24	Day 21
miTT, PP, Safety	All	Day 28	Day 25	Day 43	Day 28
miTT, PP, Safety	All	Day 60	Day 44	Day 75	Day 60
miTT, PP, Safety	All	Day 90	Day 76	Day 105	Day 90
miTT, PP, Safety	All	Day 120	Day 106	Day 135	Day 120
miTT, PP, Safety	All	Day 150	Day 136	Day 169	Day 150
miTT, PP, Safety	All	Day 180	Day 170	Day 190	Day 180
Safety OL	All	Day 180 visit + 15-21 days	Day 180 visit + 15 days	Day 180 visit + 21 days	Day 195

Note: Data collected after the nominal day 180 study visit, i.e. after the start of open label PQ for non-relapsers, will not be slotted to any visit up to and including the day 180 visit, regardless of the study day. Only the Day 195 visit window will be considered for slotting.

For all data summarised by visit, the nominal visit description will be used. Unscheduled and withdrawal visit data will be slotted into a scheduled visit window, but the data will only be included in summaries and figures if no scheduled visit exists within the same window. If there are multiple assessments within the same window which are not unscheduled visits, the earliest result will be used in the summaries and figures. If only unscheduled visits are included in the same window, the earliest of these results will be used in summaries and figures.

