**Table 2 Clinical Chemistry Tests**

Creatinine	BUN	Total bilirubin	Indirect bilirubin
AST	ALT	ALP	CPK

Urinalysis will be conducted at screening. Urine (approximately 20mL mid-stream urine) will be analyzed for protein, glucose, ketones, bilirubin, blood, nitrites and urobilinogen by dipstick method. Sediment microscopy will be performed if the leukocyte, nitrites, protein, or occult blood is abnormal and will include analysis for white blood cells, red blood cells, hyaline casts, granular casts and cellular casts.

Methemoglobin status will be assessed daily up to Day 14, on alternate days up to Day 28 and on Day 60 (or at relapse/withdrawal from study) (See Section [7.1](#)). Subjects with anemia may have symptomatic methemoglobinemia at levels lower than subjects with normal hemoglobin levels (symptoms typically do NOT occur with metHb values  $<20\%$  in subjects with normal hemoglobin levels).

All laboratory tests with values that are considered clinically significantly abnormal during participation in the study should be reported as AEs and then tests repeated until the values return to normal or baseline. If such values do not return to normal within a period judged reasonable by the investigator, the etiology should be identified and the sponsor notified.

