11.11.5. Safety Figures

Safety: Figures					
No.	Population	IDSL / Example Shell	Title	Programming Notes	Deliverable
Adverse Events					
3.1	Safety	AE10	Common ($\geq 5\%$ in Any Treatment Group) Adverse Events and Relative Risk During the Double-Blind Treatment Phase	IDSL	SAC
Laboratory					
3.2	Safety	LB11	LFT Profile Plots	
Only for subjects with >3 ULN in ALT or AST. Add footnote to this effect. The subject ID, treatment group, sex, age and race should be included as a header for each subject's plot. Include Alk. Phos, ALT, AST, Total Bili., and Indirect Bili.
	SAC
3.3	Safety	LB11	Haematology Profile Plots	
Only for subjects with a $>30\text{g/L}$ decline from baseline haemoglobin or found to be G6PD deficient Add footnote to this effect. The subject ID, treatment group, sex, age and G6PD status should be included as a header for each subject's plot. Parameters to include are haemoglobin, reticulocytes (if available), methaemoglobin and bilirubin results (total and indirect bilirubin on same plot)
	SAC

Safety: Figures					
No.	Population	IDSL / Example Shell	Title	Programming Notes	Deliverable
3.4	Safety	LB11	Clinical Chemistry Profile Plots	
Only for subjects change from baseline in urea or creatinine > 50% Add footnote to this effect.
 
The subject ID, treatment group, sex, age and race should be included as a header for each subject's plot.
 
Parameters to include are creatinine and urea (present the results relative to ULN).
	SAC
3.5	Safety	LB10	Distribution of Maximum LFTs by Treatment Group		SAC
3.6	Safety	LB7	LFT Shift from Baseline to Maximum Value		SAC
3.7	Safety	LB8	Matrix Display of Maximum LFT Values		SAC
3.8	Safety	SAFE_F1	Maximum Absolute Methaemoglobin Value Over 28 Days		SAC
3.9	Safety	LIVER14	Scatter Plot of Maximum vs. Baseline for ALT	IDSL	SAC
3.10	Safety	LIVER9	Scatterplot of Maximum ALT vs. Maximum Total Bilirubin	IDSL	SAC
Methaemoglobin					
3.11	Safety	SAFE_F2	Change from Baseline in Methaemoglobin over time	Display up to 28 days	SAC
Vital Signs					
3.12	Safety	LB9	Boxplot of Mean Arterial Blood Pressure by Timepoint and Treatment Group	IDSL Display LB9 includes the ULN and identifies subjects who have a value >2xULN. The ULN is not defined for arterial blood pressure, so this is not required. The figure should just include all of the data at each visit.	SAC

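### SAP 11.3.1 keeps one methaemoglobin value per wide window after Day 14, so most planned alternate-day readings on Days 16-28 drop out of the by-visit tables and the time-course figure

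*SAP*

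**What the plan says.** **Schedule.** The protocol text under Table 2 (Section 7.5.5) states: "Methemoglobin status will be assessed daily up to Day 14, on alternate days up to Day 28 and on Day 60". The schedule notes in SAP 11.2.1 agree: "Methemoglobin will be measured daily up to Day 14, alternate days up to Day 28 and on Day 60". Note b adds a Day 15 reading for participants who start blinded treatment on Day 2. The schedule grid also marks MetHb at the Day 21, Day 28 and Day 60 visits.

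**Windows.** In SAP 11.3.1 every day up to Day 10 has its own window, and MetHb has single-day windows of its own for Days 11, 12 and 13. The next MetHb row is "MetHB Day 14 Day 14 Day 17 Day 14" (target, start, end, label). After that MetHb falls under the rows for all parameters: "All Day 21 Day 18 Day 24 Day 21" and "All Day 28 Day 25 Day 43 Day 28".

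**Rule for several values.** Where one window holds more than one assessment that is not an unscheduled visit, "the earliest result will be used in the summaries and figures". SAP 11.6.1 repeats this for summaries and adds that all values are listed. Under 11.3.1, unscheduled data enter summaries and figures only where no scheduled visit lies in the same window.

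**Displays.** Tables 3.42 and 3.43 summarise MetHb and its change from baseline by visit. Figure 3.11 plots change over time up to 28 days. Figure 3.8 is titled "Maximum Absolute Methaemoglobin Value Over 28 Days".

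**The concern.** The SAP's authors gave MetHb day-by-day resolution while readings are daily, but did not carry this into the alternate-day period. Between Day 14 and Day 28 there is no analysis timepoint except Day 21, although readings are planned about every second day.

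Change from baseline in MetHb is a named safety endpoint in protocol Section 3 and SAP 2.2. Primaquine dosing ends on Day 14 or Day 15, so Days 16-28 are the post-dosing period for that arm, and this is the stretch that is thinned. The displays would show it at two points instead of seven or eight. On one reading of the rule, those two points would also carry labels later than the days they were measured.

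**Working it through.** The documents give no figure of their own to reproduce. The check assigns planned days to windows and counts what is kept.

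**Inputs.** Windows from SAP 11.3.1: Day 14 = 14-17, Day 21 = 18-24, Day 28 = 25-43. Schedule from the protocol text under Table 2 and SAP 11.2.1. The text says only alternate days, so the exact days are an assumption. The main case is the even grid 16, 18, ..., 28, which has (28 - 16)/2 + 1 = 7 readings after Day 14.

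**Case A: the alternate-day readings count as not unscheduled, so the earliest in each window is kept.**

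| Window | Readings in it | Kept | Dropped |
|---|---|---|---|
| Day 14 (14-17) | 14, 16 | 14 | 16 |
| Day 21 (18-24) | 18, 20, 22, 24 | 18 | 20, 22, 24 |
| Day 28 (25-43) | 26, 28 | 26 | 28 |

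Dropped: 1 + 3 + 1 = 5 of 7 (71%). The Day 21 row holds a Day 18 value (21 - 18 = 3 days early) and the Day 28 row a Day 26 value (28 - 26 = 2 days early). The Day 14 row is labelled correctly.

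Other grids under the same rule:

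| Planned days after Day 14 | Dropped | Day 21 row shows | Day 28 row shows |
|---|---|---|---|
| Even grid plus Day 21 | 6 of 8 (75%) | Day 18 | Day 26 |
| Even grid plus Days 15 and 21 | 7 of 9 (78%) | Day 18 | Day 26 |
| Odd grid 15-27 plus Day 28 | 6 of 8 (75%) | Day 19 | Day 25 |

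**Case B: the alternate-day readings are coded as unscheduled.** The scheduled Day 14, 21 and 28 visits take the rows, so the labels are right. Days 16, 18, 20, 22, 24 and 26 are excluded: 6 of 8 (75%).

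The loss of readings is therefore common to both cases. The label shift belongs to Case A only.

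**Can the dropped values be seen elsewhere?** Appendix 11 contains no listing dedicated to MetHb. Listings 28 and 29 are triggered by values of potential clinical importance, and SAP 11.8.1 sets no MetHb criterion. Figure 3.3 plots MetHb only for participants with a haemoglobin decline above 30 g/L or G6PD deficiency.

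**The case against.** **The nominal visit governs.** SAP 11.3.1 says by-visit summaries use the nominal visit description, and 11.5.2 makes planned time the default unless otherwise stated. Since MetHb is scheduled at the Day 21 and Day 28 visits, a programmer could put those readings in those rows. This stands against any claim that the rows are certain to be mislabelled: the eCRF visit coding is not in the documents, and Case B also gives correct labels. It does not rescue the interim readings. Neither the schedule grid nor the window table has a visit on Days 16, 18, 20, 22, 24 or 26, so they still have no row unless someone adds one.

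**The values are not lost.** SAP 11.6.1 does say that all values are listed. A reader might infer that the readings disappear altogether, but the documents do not support that. They drop out of summaries and figures, and the general promise of a listing is not matched by a planned MetHb listing.

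**The tafenoquine peak is covered.** Protocol Section 5.4 warns that maximal effects may come several days after dosing, because of tafenoquine's long half-life. A reader might infer that the thinning hides this peak. Tafenoquine is a single dose on Day 1 or Day 2, so several days later falls mostly where the windows are daily. That warning is not evidence of harm from the windows after Day 14.

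**Figure 3.8 is not by visit.** This is correct, and nothing says that it uses windowed data. But the earliest-result rule explicitly extends to figures, so the point needs a statement.

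**Nothing inferential depends on it.** No MetHb test is planned, and protocol Section 7.2 routes MetHb results above a preset threshold to site staff. Both points are right, and they limit the importance of the issue.

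**Conclusion.** The point holds as a minor defect in the description of a named safety endpoint. Under either coding of the interim readings, the windows leave 5 of 7 planned readings on Days 16-28 out of Tables 3.42-3.43 and Figure 3.11, or 6 of 8 when the Day 21 visit reading is counted. The proportion stays between 71% and 78% across the grids tried. This rests on two assumptions: the exact alternate days, which the documents do not give, and use of the window table as written.

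Two further consequences are conditional. The Day 21 and Day 28 rows show values 2 to 3 days early only if the interim readings count as not unscheduled. A 28-day maximum on a dropped day is missed only if Figure 3.8 follows the same rule. The documents do not establish that the rows are mislabelled, nor that peaks are lost. The primary analysis is not touched.

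**What to change.** In SAP 11.3.1, replace the rows that apply to MetHb between Day 14 and Day 43 with non-overlapping MetHb-only windows for Days 14, 15, 16, 18, 20, 21, 22, 24, 26 and 28. Keep the Day 28 window running to Day 43. One set that works is: 14; 15; 16-17; 18-19; 20; 21; 22-23; 24-25; 26-27; 28-43.

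- On the even grid with Days 15 and 21 added, all 9 readings after Day 14 are kept. On the odd grid plus Day 28, Days 15, 17, 19, 21, 23, 25, 27 and 28 each fall in a different window, so all 8 are kept.
- Where a window holds more than one value, use the one closest to target. In this set each target is the first day of its window, so the closest value is also the earliest.
- State that the alternate-day MetHb readings count as scheduled however they are recorded. SAP 11.5.2 already does this for certain laboratory results entered as unscheduled.
- State that Figure 3.8 takes the maximum of all recorded MetHb values up to Day 28, scheduled or unscheduled.

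The cost is a few more rows in the window table and longer descriptive tables, with no new data. A Day 21 or Day 28 visit held a few days early, as the visit windows allow, would be assigned to the window for the day it was taken, so those two rows may have a slightly smaller n.
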